8.7 Health Economics

Details of the Health Economics analysis will be outlined in a separate Health Economics Analysis Plan.

9. ADDITIONAL INFORMATION

9.1 Trial Steering Committee (TSC)

The TSC will provide oversight with respect to the conduct of the study on behalf of the Funder and Sponsor. An independent chair will lead the TSC, with at least 75% independent membership. Membership and roles of the TSC will be listed in the TSC Charter. The TSC will incorporate a patient/public representative as well as the CI and CL.

Doc No: ST06-RD01 Page **21** of **35** The TSC will meet at least annually and observers may be invited and be in attendance at TSC meetings, such as the Sponsor or Funder representatives or the Trial Manager to provide input on behalf of the CTU.

9.2 Data Monitoring and Ethics Committee (DMEC)

The independent DMEC will be comprised of at least 2 independent clinicians with experience in clinical trials, and an independent statistician. One of the independent clinicians will have experience in the regulatory aspects of clinical trials involving medical devices.

The role of the independent DMEC will be detailed in the DMEC charter but will include: monitoring the data and making recommendations to the TSC on whether there are any ethical or safety reasons why the trial should not continue; considering the need for any interim analysis; advising the TSC regarding the release of data and/or information; considering data emerging from other related studies. The independent DMEC will meet at least 6 monthly and additional meetings can be convened if the event of any safety concerns.

If funding is required above the level originally requested, the independent DMEC may be asked by the CI, TSC, Sponsor or Funder to provide advice and, where appropriate, information on the data gathered to date in a way that will not compromise the trial.

Doc No: ST06-RD01 Page **22** of **35**

Appendix 1: P/F ratio reference table for inclusion criteria

FiO ₂	Maximum PaO2 if P/F ratio ≤ 20kPa
0.50	10.0 kPa
0.55	11.0 kPa
0.60	12.0 kPa
0.65	13.0 kPa
0.70	14.0 kPa
0.75	15.0 kPa
0.80	16.0 kPa
0.85	17.0 kPa
0.90	18.0 kPa
0.95	19.0 kPa
1.00	20.0 kPa

Appendix 2: PEEP/FiO2 table

FiO ₂	0.3	0.4	0.4	0.5	0.5	0.6	0.7	0.7
PEEP	5	5	8	8	10	10	10	12

FiO ₂	0.7	0.8	0.9	0.9	0.9	1.0
PEEP	14	14	14	16	18	18-24

Doc No: ST06-RD01 Page **24** of **35**

APPENDIX 3: EXAMPLE DRAFT SUMMARY TABLES

Figure xxx. Recruitment by Site

Figure xxx. Withdrawals by Site

Table x.x.x. Baseline Characteristics at trial entry

Table A.A.A. Daseline Characteristics at that entry	ECCO₂R	Standard Care
	Intervention	n = (%)
	n = (%)	
Age (years)		
Gender Male		
Female		
Dependency prior to hospital admission		
Able to live without assistance in daily activities		
Minor assistance with some daily activities		
Major assistance with majority of/all daily activities		
Total assistance with all daily activities		
Height (cm) Measured length of patient (heel to crown)		
Predicted body weight (kg)		
Admission diagnostic category		
Central Nervous System		
Central Vascular System		
Respiratory System		
GIT Hepatology		
Renal		
Toxicology		
Haematology		
Orthopaedic		
Sepsis		
Other		
Presence of ARDS		
Aetiology of ARDS		

	ECCO₂R	Standard Care
	Intervention	n = (%)
	n = (%)	
Smoke/toxin inhalation		
Gastric content aspiration		
Near drowning		
Thoracic trauma		
Pneumonia		
Sepsis		
Cardiopulmonary bypass		
Pancreatitis		
Non-thoracic trauma		
Other		
APACHE II score		
Arterial blood gas PaCO ₂		
PaO ₂ :FiO ₂ ratio		
Worst PaO ₂ /FiO ₂ ratio		
Second qualifying PaO ₂ /FiO ₂ ratio		
Arterial pH		
Total SOFA Score		
Mode of Ventilation		
Mandatory, no spontaneous additional breaths above		
the fixed respiratory rate		
Spontaneous, no back up mandatory breaths		
Mixed, Mandatory and spontaneous breaths		
Other		
Use of Adjunctive therapies		
NMBD		
PP		
INO		
Other		
Mean airway pressure (cmH ₂ O)		
PEEP (cmH ₂ O)		
Plateau Pressure (cmH₂O)		

Doc No: ST06-RD01 Page **26** of **35**

	ECCO ₂ R Intervention n = (%)	Standard Care n = (%)
Total Respiratory Rate (Breaths/min)		
Minute volume (mL/min)		
Tidal Volume (mls/kg PBW)		

Mean (SD) presented for continuous variables and no. (%) for all categorical variables.

Table x.x.x. Treatment after Trial Entry

	ECCO₂R	Standard Care
	Intervention	n = (%)
	n = (%)	
Treatment Allocation		
Adherence to protocol-specified intervention		
No. of days on ECCO₂R*		
Reasons for ECCO ₂ R Discontinuation		
The patient's legal representative has requested		
witdrawal from the study		
There has been a safety concern about the therapy		
such that withdrawal is mandated		
 ECCO₂R therapy has been weaned 		
 7 days post randomisation 		
Escalation to ECMO has occurred		
Discontinuation of active medical treatment has		
occurred		
The patient has died		
Other		
Protocol Deviations:		
Eligibility		
Treatment		
Process		
Other		

^{*}Mean (SD) no. of days on ECCO₂R

Doc No: ST06-RD01 Page **28** of **35**

Table x.x.x Main Clinical Outcome variables

	ECCO₂R Intervention n = (%)	Standard Care n = (%)	Difference (95% CI)	p-value
Primary outcome; Mortality 90 days				
post randomisation#				
VFDs 28 days post randomisation				
Ventilation duration post				
randomisation				
All				
Survivors				
Non-survivors				
Need for ECMO to day 7				
Yes				
No [#]				
Mortality rate at 28 days post				
randomisation [#]				
Mortality rate at 6 months post				
randomisation [#]				
Mortality rate at 1 year post				
randomisation [#]				
SGRQ				
Symptoms Score				
Activity Score				
 Impacts Score 				
Total Score				
Need for home oxygen at 1 year post				
randomisation#				
PTSS-14 Score				
MoCA-Blind				
AD8 Dementia Screening				

Mean (SD) presented for treatment arms

Figure x.x.x. Kaplan Meier Curve

Time to death and no. of deaths on x-axis

Doc No: ST06-RD01 Page **29** of **35**

^{*}No. (%) for treatment arms and Risk Ratio and 95% CI presented

Table x.x.x. Tidal Volume after Randomisation

	ECCO₂R Intervention n = (%)	Standard Care n = (%)	Mean Difference (95% CI)
Tidal volume ml/kg PBW			
Day 2			
Day 3			
Day 4			
Day 5			
Day 6			
Day 7			
Tidal volume ml/kg PBW*			
Day 2			
Day 3			

Mean (SD) and Min/Max presented for TV and no. (total % out of 40) for recruitment rate.

Doc No: ST06-RD01 Page **30** of **35**

^{*}Per protocol population i.e. those who were on VV-ECCO₂R on day 2 and 3 in the intervention arm

Table x.x.x. Safety by Treatment Group

		Number of events			Number of patients			
		Total n	Intervention ECCO ₂ R n (%)	Standard Care n (%)	Total n (%)	Intervention ECCO ₂ R n (%)	Standard Care n (%)	RR(95%CI)
AEs, SAEs, ADE, SADE, USADE	Total SAEs							
	Related to study device							
	Related to study device and unanticipated							
	Total AEs							
	Related to study device							
SAEs	Cardiac Disorders							
	Hepatobiliary disorders							
	Respiratory, thoracic and mediastinal disorders							
	etc							
AEs	Device failure causing AE							
	Haemolysis							
	Bleeding at cannula site							
	Bleeding at other site							
	Infectious complications							
	Heparin induced thrombocytopenia							
Adverse Device effect								
Serious Adverse Device effect								

The REST Trial STATISTICAL PLAN (Final version 1.0, 16/12/19)

Unanticipated				
Serious Adverse				
Device effect				

For no. of events %s are calculated within total SAEs, AEs, ADEs and SADEs respectively within treatment arm.

Doc No: ST06-RD01 Page **32** of **35**

Table xxx. Follow-up Questionnaires at 1 year

	ECCO₂R Intervention n = (%)	Standard Care n = (%)	Difference (95% CI)
Saint Georges			
Questionnaire			
PTSS-14			
MoCA			
AD8			

Figure x.x.x. Subgroup Analyses

OR and 99% CI will be presented graphically alongside the n(%) for interaction terms for the following pre-specified subgroups

	Treatment Group			
	Intervention ECCO ₂ R	Standard Care	Difference (99% CI)	
Presence of ARDS prior to randomisation				
Yes				
No				
Baseline PaO ₂ /FiO ₂ ratio prior to randomisation				
<50				
50-99				
100-150				
Baseline Plateau Pressure prior to randomisation				
Quartile 1				
Quartile 2				
Quartile 3				
Quartile 4				
Volume of ECCO₂R participants at center				
<10 cases				
>=10 cases				

Doc No: ST06-RD01 Page **33** of **35**

The REST Trial STATISTICAL PLAN (Final version 1.0, 16/12/19)

	Treatment Group		
	Intervention ECCO ₂ R	Standard Care	Difference (99% CI)
Vasopressor requirement prior to randomisation			
Yes			
No			
Baseline PaCO ₂ prior to randomisation			
Quartile 1			
Quartile 2			
Quartile 3			
Quartile 4			
Duration of Carbon Dioxide (CO ₂) removal			
Quartile 1			
Quartile 2			
Quartile 3			
Quartile 4			
Baseline driving pressure prior to randomisation			
Quartile 1			
Quartile 2			
Quartile 3			
Quartile 4			
Baseline risk of death score (Apache II) quintiles prior to			
randomisation			
Quintile 1			
Quintile 2			
Quintile 3			
Quintile 4			
Quintile 5			

Table x.x.x. Exploratory Outcome Measures

	Treatment Group		
	Intervention ECCO₂R	Standard Care	Difference (99% CI)
Baseline / Day 0:			
 Tricuspid annular plane systolic excursion (TAPSE) measured in cm Right ventricular strain (RVS) measured in percentage Right ventricle fractional area of change (FAC) measured in percentage Right ventricle end diastolic area to Left ventricle end diastolic ratio (EDA ratio) measure as a ratio (e.g. 0.6) Left ventricular end diastolic diameter measured in cm Left ventricle function measured in percentage 			
Day 1 or 2:			
 TAPSE measured in cm RVS measured in percentage Right Ventricle FAC measured in percentage Right ventricle EDA ratio Left ventricle end diastolic diameter measured in cm Left ventricle function measured in percentage 			

Doc No: ST06-RD01 Page **35** of **35**

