2.2 Secondary outcome measures

- I. Tidal volume (ml/kg PBW) at day 2 and day 3 after randomisation
- II. Ventilator free days at 28 days after randomisation
- III. Duration of ventilation in survivors after randomisation at 28 days
- IV. Need for ECMO up to Day 7
- V. Mortality rate at 28 days, 6 months and 1 year after randomisation
- VI. Health Related Quality of Life (HRQoL) at 6 months and 1 year after randomisation
- VII. Adverse event rate
- VIII. Health & Social Care Service costs at 6 months and 1 year
 - IX. St George's Respiratory Questionnaire (SGRQ) at 1 year and need for home oxygen at 6 months and 1 year after randomisation
 - X. Post Traumatic Stress Syndrome Questionnaire (PTSS-14) at 1 year after randomisation
- XI. Montreal Cognitive Assessment (MoCA-BLIND) or AD8 Dementia Screening Interview (AD8) at 1 year after randomisation

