3.5 Data coding

The variable codings will be as specified on the CRF.

4. **DEFINITION OF TERMS**

Term	Definition
Discharge from	First discharge to a medical ward in the hospital or another hospital;
critical care	a transfer between ICUs is not considered a discharge from critical
	care.
Hospital discharge	Hospital discharge is the first date that the patient is discharged to
	home/ community, a transfer between hospitals is not considered
	as a hospital discharge
Unassisted	Extubated with supplemental oxygen, or room air, or open T-tube
breathing i.e. no	breathing, or tracheostomy mask breathing, or CPAP \leq 5 cm H ₂ O
ventilatory support	without pressure support for a calendar day. Patients receiving
	pressure support via non-invasive ventilation will be defined as
	receiving ventilatory support (except for sleep disordered
	breathing).
VFDs to day 28	The number of days from the time of initiating unassisted breathing
	to day 28 after randomisation, assuming survival for at least two
	consecutive calendar days after initiating unassisted breathing and
	continued unassisted breathing to day 28. If a patient returns to
	assisted breathing and subsequently achieves unassisted breathing

Doc No: ST06-RD01 Page **13** of **35** to day 28, VFDs will be counted from the end of the last period of assisted breathing to day 28. A period of assisted breathing lasting less than 24 hours and for the purpose of a surgical procedure will not count against the VFD calculation. If a patient was receiving assisted breathing at day 27 or dies prior to day 28, VFDs will be zero. Patients transferred to another hospital or other health care facility will be followed to day 28 to assess this endpoint.

Duration of ventilation

Counted from recruitment to the end of the last period of assisted breathing

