8.5 Trial Outcomes

- All-cause mortality 90 days after randomisation, no (%) by treatment arm, Risk ratio 95%
- Tidal Volume (ml/kg PBW) at days 2 and 3 after randomisation, mean (SD) by treatment arm, difference in mean with 95% CI
- Ventilator free days at 28 days after randomisation, mean (SD) by treatment arm,
 difference in mean with 95% CI
- Ventilation duration in survivors after randomisation at 28 days, mean (SD) by treatment arm, difference in mean with 95% CI
- Need for ECMO up to day 7, no (%) by treatment arm, Risk ratio 95% CI
- Mortality rate at 28 days after randomisation, no (%) by treatment arm, Risk ratio 95%
- Mortality rate at 6 months after randomisation, no (%) by treatment arm, Risk ratio 95%
- Mortality rate at 1 year after randomisation, no (%) by treatment arm, Risk ratio 95% CI
- SGRQ at 1 year after randomisation, Symptoms score, Activity score, Impacts score and
 Total score mean (SD) by treatment arm, difference in mean with 95% CI
- Need for home oxygen at 6 months and 1 year after randomisation, no (%) by treatment arm, Risk ratio 95% CI
- Post Traumatic Stress Syndrome Questionnaire (PTSS-14) at 1 year after randomisation,
 mean (SD) by treatment arm, difference in mean with 95% CI
- Montreal Cognitive Assessment (MoCA-BLIND) or AD8 Dementia Screening Interview (AD8) at 1 year after randomisation, mean (SD) by treatment arm, difference in mean with 95% CI
- Right heart function as determined by echocardiography during 6ml/kg PBW and
 ≤3ml/kg PBW tidal volume ventilation. Echocardiography parameters including but not
 limited to ventricular size and function and TAPSE, mean (SD) by treatment arm,
 difference in mean with 95% CI

Doc No: ST06-RD01 Page **20** of **35**

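### The example outcome table adds between-arm contrasts of ventilation duration in all patients and in non-survivors, which the analysis text does not plan and which early deaths on the ventilator could make look favourable

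*SAP*

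**What the plan says.** The SAP names this outcome in section 2.2 (III) as "Duration of ventilation in survivors after randomisation at 28 days". Section 8.5 repeats the restriction, "Ventilation duration in survivors after randomisation at 28 days, mean (SD) by treatment arm", and adds a difference in means with 95% CI. Neither section plans a comparison in all patients or in those who died.

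The shell for the main clinical outcomes in Appendix 3 goes further. Under the row label that begins "Ventilation duration post" it has three sub-rows: all patients, survivors and "Non-survivors". The table has one column whose heading begins "Difference (95% CI" and another for the p-value. Its footnote gives mean (SD) as the summary by arm.

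Section 4 defines the duration as "Counted from recruitment to the end of the last period of assisted breathing". It does not say what happens when a patient dies while ventilated. For ventilator-free days (VFDs) the same section does give a rule: if a patient "dies prior to day 28, VFDs will be zero".

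**The concern.** For a patient who dies while ventilated, the last period of assisted breathing ends at death. With no other rule in section 4, that patient's duration is the time to death, and a very early death gives a very short value. In a comparison of mean duration, short is the favourable direction.

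Two consequences follow if the shell is filled in as drawn. First, the all-patient difference mixes faster weaning with earlier death and cannot tell them apart, so an arm with more early deaths could appear to need less ventilation. Second, the non-survivor difference compares groups formed by an event after randomisation. If treatment changes who dies or when, the two groups of deaths are not comparable.

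What is at stake is limited but visible. The main results table could carry an interval and a p-value for a contrast that section 8.5 does not plan, and that contrast could point the opposite way from VFDs in the same table.

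**Working it through.** The SAP states no figure for this point, so there is nothing to reproduce. The check is a reading of the sections followed by arithmetic for scale.

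**Sections side by side**

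| Place in the SAP | Population for ventilation duration | Between-arm comparison | Rule for death |
|---|---|---|---|
| 2.2 (III) | survivors | – | – |
| 4 | not restricted | – | none for duration; zero for VFDs |
| 8.5 | survivors | difference in means, 95% CI | – |
| Appendix 3 | all, survivors, non-survivors | difference, 95% CI, p-value | – |

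Section 7 assigns survival methods to time-to-event outcomes. Section 8.5 and the table footnote treat duration as a mean, so no competing-event method applies to these rows.

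**Inputs**
- Control mortality 41% and an absolute effect of 9 percentage points: SAP section 5. These are 90-day figures, used here only to set the size of the competing event.
- Mean ventilation Vs = 12 days in survivors (range 10 to 14) and Vd = 8 days in non-survivors (range 4 to 10): assumed, not in the SAP.
- No effect of treatment on weaning: assumed, to isolate the effect of deaths.

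**All patients, extra deaths with the same mean duration as other deaths**

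Mean = (1 − m) × Vs + m × Vd
- m = 0.41: 0.59 × 12 + 0.41 × 8 = 10.36 days
- m = 0.50: 0.50 × 12 + 0.50 × 8 = 10.00 days, so 0.36 day shorter with higher mortality
- m = 0.32: 0.68 × 12 + 0.32 × 8 = 10.72 days, so 0.36 day longer with lower mortality

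The shift is 0.09 × (Vd − Vs). It runs from 0.09 × (10 − 10) = 0 to 0.09 × (4 − 14) = −0.9 day.

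**All patients, every extra death on the ventilator at day e**

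Shift = 0.09 × (e − Vs)
- e = 4, Vs = 10: −0.54 day
- e = 2, Vs = 14: −1.08 days

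The sign depends on e. The shift is zero at e = Vs and positive if the extra deaths come later than weaning would have.

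**Non-survivors, same early deaths**

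Shift = (0.41 × 8 + 0.09 × e) / 0.50 − 8
- e = 2: 6.92 − 8 = −1.08 days
- e = 4: 7.28 − 8 = −0.72 day

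**Simulation as a cross-check**

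Durations were exponential and capped at day 28, with means for survivors/deaths of 8/6, 12/10 and 16/14 days (assumed). All deaths were on the ventilator, and 9 points of extra deaths were spread evenly over days 0 to 4.

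| Means (days) | All | Survivors | Non-survivors | VFDs |
|---|---|---|---|---|
| 8/6 | −0.52 | −0.01 | −0.70 | −1.80 |
| 12/10 | −0.80 | 0.00 | −1.33 | −1.55 |
| 16/14 | −1.02 | −0.01 | −1.82 | −1.32 |

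The first and third contrasts look favourable, the planned survivor contrast does not move, and VFDs show the harm. With 543 evaluable per arm (560 × 0.97), z is −1.31 to −1.76 for all patients and −1.39 to −2.17 for non-survivors.

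**Scale of the simple case**

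With an assumed SD of 8 to 10 days, the standard error of a difference is SD × √(2/543), which is 0.49 to 0.61 day. A shift of 0.36 day then gives z of about 0.6 to 0.7.

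**The case against.** The strongest reply is about status. The two rows occur only in an appendix of example draft tables. The sections that fix the analysis restrict the outcome to survivors. The shells also show more than the text lists elsewhere: tidal volume runs to day 7, while section 8.5 names days 2 and 3. The difference and p-value headings span the whole table, including both the yes and no rows for ECMO, so empty cells do not prove that a test is intended in each sub-row. Section 7 sets a significance level for the primary outcome only and promises estimates with 95% CIs for the rest. All of this stands, and it is why the point is minor. It does not remove the mismatch: the SAP is marked final, and a shell filled in as drawn would produce these contrasts.

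The second reply is that the safeguard is already present. VFDs, with death scored as zero, sit directly above these rows, and mortality at four time points is in the same table. A careful reader would see both. This also stands: it limits the risk of misreading, though it gives the two contrasts no valid interpretation of their own.

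The third reply is that the sizes are wholly assumed, that the simple case is small with a range that includes zero, and that the larger figures need all the extra deaths to come in the first days with weaning unchanged. That is correct.

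A reader might infer something stronger: that the SAP deliberately counts death as early liberation, or that the table would show benefit for a harmful device. The document supports neither. That death ends the count is an inference from a definition that is silent on it, and the direction depends on when deaths occur. A reader might also say that the non-survivor row splits patients by the primary outcome. The shell does not say whether survival is judged at day 28 or day 90, so only the weaker statement holds: the split is on a post-randomisation event.

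**Conclusion.** The point holds as a minor matter of consistency and bias. Appendix 3 displays two between-arm contrasts that sections 2.2 and 8.5 do not plan. With no death rule in section 4, the all-patient contrast could favour an arm with more early deaths, and the non-survivor contrast has no randomised interpretation.

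The size is illustrative. The figures of 0.36 day (range 0 to 0.9) and of 0.5 to 1.1 days rest on assumed durations, on 9 extra points of mortality and on no effect on weaning; the larger range also needs all the extra deaths on days 2 to 4. Late deaths would shrink or reverse the shift.

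The primary outcome and every named secondary outcome are untouched. The survivor row also conditions on a post-randomisation event, but it is the named outcome and is not the subject of this point.

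**What to change.** Delete the all-patient and non-survivor rows so that the shell matches section 8.5. Alternatively, keep them as descriptive summaries by arm, with the difference, CI and p-value cells blanked. If they stay, add a footnote saying how death enters the duration and at which day survivor status is judged. Rely on VFDs, already planned with death scored as zero, for the all-patient comparison.

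Optionally, show the cumulative incidence of unassisted breathing to day 28 by arm, with death as a competing event. Section 3.3 already collects the dates of ventilation discontinuation and of death.

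The cost is one edit to a table shell. The small downside is the loss of a familiar contrast that some readers may expect to see.

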1.4 Exclusion criteria

- Age < 16 years old
- Intubated and mechanically ventilated via an endotracheal or tracheostomy tube ≥ 7
 days (168 hours) up to the time of randomisation
- Ability to maintain Vt to ≤ 3ml/kg PBW while maintaining pH ≥ 7.2 as determined by the treating physician*
- Receiving, or decision to commence, ECMO in the next 24 hours.
- Mechanical ventilation using High Frequency Oscillatory Ventilation (HFOV) or Airway Pressure Release Ventilation (APRV)
- Untreated pulmonary embolism, pleural effusion or pneumothorax as the primary cause of acute respiratory failure.

Doc No: ST06-RD01 Page **6** of **35**

^{*}Recommended on low tidal volume ventilation ≤ 6ml/kg PBW

^{**}Requires two ABG with a PaO2/FiO2 \leq 20kPa separated by at least 6 hours. 48 hour duration to consent begins at the time of 2nd ABG demonstrating PaO2/FiO2 ratio \leq 20kPa. Site will then have a further 8 – 24 hours to randomise and administer the intervention. The onset of hypoxaemia is from time of intubation and invasive ventilation.(ABGs with PaO2/FiO2 \geq 20kPa are permitted between the two trial inclusion ABGs).

- Acute respiratory failure fully explained by left ventricular failure or fluid overload (May be determined by clinical assessment or echocardiography/cardiac output monitoring).
- Left ventricular failure requiring mechanical support
- Contra-indication to limited systemic anticoagulation with heparin
- Unable to obtain vascular access to a central vein (internal jugular or femoral vein)
- Inferior vena cava filter (if using femoral vein catheter)
- Consent declined
- Treatment withdrawal imminent within 24 hours
- Patients not expected to survive 90 days on basis of premorbid health status
- Do Not Attempt Resuscitation (DNAR) order (excluding advance directives) in place
- Severe chronic respiratory disease requiring domiciliary ventilation (except for sleep disordered breathing)
- Severe chronic liver disease (Child Pugh >11)
- Platelet count < 40,000 mm³ (Prior to catheter insertion)
- Previously enrolled in the REST trial
- Prisoners

[figure not shown]
Full details of the background to the trial and its design are presented in the protocol.

Doc No: ST06-RD01 Page **7** of **35**

^{*} This exclusion criterion relates to whether a Vt \leq 3ml/kg PBW could be achieved without the need for ECCO₂R. A tidal volume \leq 3ml/kg is unlikely to be achievable in most clinical scenarios without ECCO₂R as it is approaching dead space ventilation.

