- CO₂ removal rate while on ECCO₂R therapy
- Commencement or transfer for ECMO following randomisation
- Use of adjunctive therapies including NMBD and prone positioning
- Blood product administration (blood, platelets, fresh frozen plasma, cryoprecipitate or other)
- Adverse events

Day 1 and 2:

Echocardiography parameters including but not limited to ventricular size and function and TAPSE.

Doc No: ST06-RD01 Page **11** of **35**

Day 3 and 7

• Determinants of SOFA score

28 days:

Adverse Events

6 months:

- EuroQoL-5 Dimension Questionnaire (EQ-5D-5L) (Post or telephone)
- Patients use of health and social care resources collected by resource logs

1 year:

- EQ-5D-5L (Post or telephone)
- Patients use of health and social care resources collected by resource logs
- SGRQ
- PTSS-14
- MoCA-Blind or AD8

The following data will also be collected

- Date of discontinuation of ECCO₂R and reason
- Date of discontinuation of mechanical ventilation (unassisted breathing)
- Date of critical care discharge
- Date of hospital discharge
- Date of death

Follow Up Visits and Procedures

HRQoL and Health and Social Care Service use will be assessed at 6 months and 1 year after randomisation. Patients will also be required to complete the SGRQ at 1 year.

The CTU will also collect mortality data at 1, 2 and 5 years post randomisation.

Doc No: ST06-RD01 Page **12** of **35**

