8.6 Toxicity/ Symptoms

• Adverse Event Rate, no. events (%) by treatment arm , no. patients (%) by treatment arm. Risk Ratio and 95% CI.

AEs of interest are as follows:

Device failure causing AE Haemolysis Bleeding

At cannula site

Other site

Infectious complications

Heparin induced thrombocytopenia

- Adverse Device Effect, no. events (%) by treatment arm, no. patients (%) by treatment arm. Risk Ratio and 95% CI.
- Serious Adverse Event, no. events (%) by treatment arm and System Organ Class, no.
 patients (%) by treatment arm. Risk Ratio and 95% CI.
- Serious Adverse Device Effect, no. events (%) by treatment arm and System Organ Class, no. patients (%) by treatment arm. Risk Ratio and 95% CI.
- Unanticipated Serious Adverse Device effect, no. events (%) by treatment arm and
 System Organ Class, no. patients (%) by treatment arm. Risk Ratio and 95% CI.

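### No stated line compares serious bleeding between arms, so an excess would be diluted, either among minor bleeds or across organ classes

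*SAP*

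**What the plan says.** Section 8.6 lists bleeding among the adverse events of interest and divides it by place only: cannula site or elsewhere. The safety table in Appendix 3 repeats this as two rows of its AE block, "Bleeding at cannula site" and "Bleeding at other site". Neither place has a severity grade, a count of serious bleeds or an intracranial row.

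Serious events follow a different structure. Section 8.6 specifies "Serious Adverse Event, no. events (%) by treatment arm and System Organ Class", and does the same for device effects: "Serious Adverse Device Effect, no. events (%) by treatment arm and System Organ Class, no. patients (%) by treatment arm". Each comes with a risk ratio and 95% CI. The table's SAE block names three organ classes and then leaves the list open. It has no haemorrhage row.

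The SAP treats bleeding as foreseeable. Section 1.4 excludes patients with "Contra-indication to limited systemic anticoagulation with heparin" and those with low platelets, and section 1.2 makes safety a secondary objective (vi). Section 3.3 has blood product use recorded daily to day 7, but neither 8.5, 8.6 nor the Appendix 3 tables has a line for it.

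**The concern.** The two structures do not meet. The bleeding rows have site but no seriousness, and the SAE rows have seriousness but do not group bleeding. The SAP does not say how the two blocks relate, which leaves two readings:

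- **AE rows include SAEs.** A serious non-cannula bleed is counted in the other-site row together with every minor one.
- **AE rows exclude SAEs.** Serious bleeds are absent from the bleeding rows. They appear only under nervous-system, gastrointestinal, respiratory and other classes, next to events that are not bleeds.

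Under either reading, a reader of the final report who asks how many patients per arm had a serious bleed finds no pre-specified answer. A grouping assembled after the data are seen, in a trial that section 6.2 describes as open to care providers, outcome assessors and analysts, carries less weight, whether it shows harm or reassures.

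**Working it through.** The SAP states no bleeding figure, so there is nothing to reproduce. The check is textual (above), followed by an illustration of how much the grouping matters.

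**Inputs.** 560 patients per arm (section 5) and 1:1 allocation (section 6.1). All event rates are assumptions:
- serious bleeding *s* of 2.0% with the device and 0.2% with standard care;
- other non-cannula bleeding *b* of 5%, 8% or 12% in both arms;
- other nervous-system SAEs *b* of 0.5%, 1% or 2% in both arms.

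**Method.** A patient may have both kinds of event, so the proportion in a combined row is 1 − (1 − s)(1 − b). The last column is the probability that Fisher's exact test (two-sided 0.05) shows an excess in the device arm, summed exactly over the binomial counts.

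| Row | Device | Control | Risk ratio | p<0.05 |
|---|---|---|---|---|
| Serious bleeding alone | 2.00% | 0.20% | 10 | 82% |
| Other site, b = 5% | 1 − 0.98×0.95 = 6.90% | 1 − 0.998×0.95 = 5.19% | 1.33 | 19% |
| Other site, b = 8% | 9.84% | 8.18% | 1.20 | 13% |
| Other site, b = 12% | 13.76% | 12.18% | 1.13 | 10% |
| Nervous-system SAE, b = 0.5% | 2.49% | 0.70% | 3.56 | 60% |
| Nervous-system SAE, b = 1% | 2.98% | 1.20% | 2.49 | 48% |
| Nervous-system SAE, b = 2% | 3.96% | 2.20% | 1.80 | 34% |

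The nervous-system rows take all the serious bleeds as intracranial. Simulation of the same settings gives about 81%, 11–20% and 35–59% for the three groups of rows. These are the figures used in the summary and conclusion, and the two methods agree to about a point.

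**In the table's own terms.** The safety table shows a risk ratio and CI, so take expected counts rounded to whole patients, with SE(log RR) = √(1/a + 1/c − 2/560):
- Dedicated row, 11 v 1: RR 11, SE 1.04, 95% CI about 1.4 to 85.
- Other-site row at b = 8%, 55 v 46: RR 1.20, SE 0.19, 95% CI about 0.8 to 1.7.

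**A smaller relative excess.** At 2.0% v 0.5%, the dedicated row reaches p<0.05 in about 54% of trials and the pooled row in about 14%, 10% or 8%.

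**Scatter across classes.** Take serious bleeding of all kinds at 4% v 1%, with normal-approximation power.
- A dedicated row has RR 4.0 and power of about 90%.
- Pooled with minor other-site bleeding of 5%, 10% or 20%, counts added without overlap, RR = (0.04 + b)/(0.01 + b) = 1.50, 1.27 or 1.14. Power is about 48%, 33% or 22%.
- Split evenly over three organ classes, power is about 45% per class. If each class also holds 3% of other SAEs, RR = (0.04/3 + 0.03)/(0.01/3 + 0.03) = 0.0433/0.0333 = 1.30, and power is about 14%.

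**The case against.** The strongest reply is that nothing here is misstated. The Appendix 3 tables are headed as example drafts and the SAE list is left open. Grading and AE/SAE definitions may sit in the protocol. SAEs by organ class already come with patient-level risk ratios, and a data monitoring committee reviews safety at least every six months.

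Much of that stands, and it limits the point. Three stronger readings are tempting but not supported:

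- **The plan pools a trivial bleed with an intracranial one.** The SAP never says the other-site row includes SAEs. The table has separate AE and SAE blocks with separate totals, so they may be disjoint, in which case the pooled-row figures do not arise and the organ-class figures apply.
- **The plan could return a near-null result while serious bleeding is in excess.** That describes one row. An all-intracranial excess would still give a risk ratio of about 1.8 to 3.6 in the nervous-system SAE row on the assumed rates. The scatter argument fits serious bleeding overall better than intracranial bleeding alone.
- **Blood product data go unanalysed.** Section 7 commits to describing follow-up measurements and safety data, which covers them in general terms, although no line is named. Transfusion is also decided by unblinded clinicians, so it is not an unbiased substitute for AE reports.

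The safety table has no p-value column, and the only stated significance level is for the primary outcome. The p<0.05 frequencies therefore measure dilution and do not describe planned tests. The SAP also does not rank harms, so calling bleeding the main risk goes beyond the text.

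What the reply does not meet is that section 8.6, in the body of the SAP, fixes the same categories as the draft table. Grading at collection, wherever it is defined, does not create an analysis line.

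**Conclusion.** The point holds as a reporting gap. No stated line compares serious bleeding, or intracranial haemorrhage, between arms, and the relation between the AE bleeding rows and the SAE rows is undefined. An excess would be diluted, not hidden. On the assumed 2.0% v 0.2% with 560 per arm, a dedicated row would reach p<0.05 in about 81% of trials, against about 11–20% for a pooled other-site row and about 35–59% for a nervous-system SAE row if all events were intracranial. These sizes rest on assumed rates and on the planned sample size. The pooled figure applies only if the AE rows include SAEs. The primary result is unaffected; what is weakened is the answer to safety objective (vi). The change should be made, but it is a refinement and not the correction of an error.

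**What to change.** In section 8.6 and the safety table:

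1. State whether the AE bleeding rows include events also recorded as SAEs.
2. Add a row for any serious bleeding, drawn from AE and SAE records with all System Organ Classes combined.
3. Add a row for intracranial haemorrhage, where the site can be recovered from the AE and SAE records.
4. Report both new rows as patients (%) of those randomised in each arm, with risk ratio and 95% CI. The note under the safety table bases event percentages on total events within the arm, so event counts alone would not serve.
5. Optionally, add patients (%) given any blood product to day 7, by arm, as a supporting description, noting that transfusion is also given unblinded.

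This changes SAP and table wording and regroups records already planned. The CRF is not shown, so whether bleeding site and seriousness can be recovered for every event needs checking. The downside is a few more rows, some with sparse counts and wide intervals.
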